6. TREATMENT DESCRIPTION

All analysis will be described for patients with Crohn's Disease and Ulcerative Colitis separately.

6.1. Biological treatment

We will describe the treatments administered to the patients:

- Number and percentage of patients who received each biological treatment (infliximab, adalimumab, golimumab and others).
- Number and percentage of patients who intensified the biological treatment and the reason (increased doses, decreased intervals between doses or both) according to the different biological treatment specified.
- Number and percentage of patients who discontinued the treatment and the reason (PNR, LOR, PR, SE, remission and others) according to the different biological treatment specified.
- Number and percentage of patients who received a second biological treatment and the description of the different biological treatments and the number of biological treatments received after discontinuation.
- Number and percentage of patients who received concomitant treatment with corticosteroids or immunosuppressives during induction phase. Description of the different concomitant treatment received.

6.2. Treatments received before the reference period

- Number and percentage of patients who received at least one treatment before the reference period.
 - Number and percentage of patients who received aminosalicylates and the description of the treatments received (mesalazine, sulfasalazine, others).
 - Number and percentage of patients who received corticosteroids and the description of the treatments received (prednisone, hydrocortisone, methylprednisolone, Beclomethasone, budesonide, others).
 - Number and percentage of patients who received Immunosuppressives and the description of the treatments received (cyclosporin, methotrexate, azathioprine, mercaptopurine, others).
 - Number and percentage of patients who received anti-diarrheal drugs.
 - Number and percentage of patients who received pain medications.
 - Number and percentage of patients who received antidepressants.
 - Number and percentage of patients who received antibiotics.

- Number and percentage of patients who used alternative medicine and the description of the therapy received (acupuncture, relaxation therapy, Qigong, herbal therapy, others).
- Number and percentage of patients who received cannabis.
- Number and percentage of patients who received other treatments and the description of the treatment received.

6.3. Treatments received during the reference period (maintenance phase).

- Number and percentage of patients who received at least one concomitant treatment during the reference period (maintenance phase).
 - Number and percentage of patients who received aminosalicylates and the description of the treatments received (mesalazine, sulfasalazine, others).
 - Number and percentage of patients who received corticosteroids and the description of the treatments received (prednisone, hydrocortisone, methylprednisolone, Beclomethasone, budesonide, others).
 - Number and percentage of patients who received Immunosuppressives and the description of the treatments received (ciclosporin, methotrexate, azathioprine, mercaptopurin, others).
 - Number and percentage of patients who received anti-diarrheal drugs.
 - Number and percentage of patients who received pain medications.
 - Number and percentage of patients who received antidepressants.
 - Number and percentage of patients who received antibiotics.
 - Number and percentage of patients who used alternative medicine and the description of the therapy received (acupuncture, relaxation therapy, Qigong, herbal therapy, others).
 - Number and percentage of patients who received cannabis.
 - Number and percentage of patients who received others treatments and the description of the treatment received.

7. EFFICACY ASSESSMENT

7.1. Efficacy Assessment; general considerations

Non responders will be those patients not achieving a reduction in HBI of at least 2 points from baseline for CD and a decrease in the PMS of at least 2 points for UC.

In the cases where these indexes are not available, clinical response will be evaluated according to physician criteria at short term (10 weeks after starting the anti-TNF [*primary response and primary non-response*]) and at long term (at least 6 months after starting the anti-TNF [*primary response maintenance and loss of response*]).

We will calculate the following variables:

- **Lack response during the induction phase (primary non response):** Those patients who 10 weeks after starting the anti-TNF not achieving a reduction in HBI of at least 2 points from baseline for CD and a decrease in the PMS of at least 2 points for UC. In the cases where these indexes are not available, clinical response will be evaluated according to physician criteria at short term (*primary response and primary non-response*).
- **Loss of response during the maintenance phase (secondary loss of response):** Those patients who at least 6 months after starting the anti-TNF not achieving a reduction in HBI of at least 2 points from baseline for CD and a decrease in the PMS of at least 2 points for UC. In the cases where these indexes are not available, clinical response will be evaluated according to physician criteria at short term (*primary response maintenance and loss of response*).

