#### **6.3.2. Inclusion criteria**

- Adult patients (aged  $\geq 18$ )
- Patients diagnosed with UC or CD according to the "World Gastroenterology Organization Practice Guidelines for the Diagnosis and Management of IBD in 2010"
- Patients naive to biologics that started treatment with biologics between June 2011 and June 2013
- Patients in whose biological treatment was prescribed according to daily clinical practice.
- Patients that gave written informed consent

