#### 6.4.4. Study variables

The following **sociodemographic variables** will be collected from patients' medical records or directly from patients during the study visit, straight after their inclusion in the study:

- Age
- Gender
- Race (caucasian, asiatic, latin, black, other)
- Level of education (uneducated, primary education, secondary education, university education)
- Working status (student, self-employed, employed by other, retired, housework, unemployed, temporarily unable to work, permanently unable to work, other)
- Smoking habits (non-smoker, ex-smoker, smoker, number of cigarettes per day)
- Alcohol intake (units per week).

The following **clinical variables** will be collected from patients' medical records (when available) or directly from patients during the study visit, straight after their inclusion in the study:

- Date of diagnosis (UD or CD).
- Disease activity at the beginning of the reference period and at the study visit through collection of the following variables:
  - For UC patients:
    - Partial Mayo Score (PMS) (9 point scale that excludes the endoscopic appearance of the mucosa)
    - General disease activity:
      - Mild: up to four bloody stools daily and no systemic toxicity
      - Moderate: four to six bloody stools daily and minimal toxicity
      - Severe: more than six bloody stools daily and signs of toxicity, such as fever, tachycardia, anaemia, raised erythrocyte sedimentation rate.
      - Fulminant: More than ten bloody stools daily, continuous bleeding, anaemia requiring blood transfusion, abdominal tenderness and colonic dilatation on plain abdominal radiographs.
    - Disease anatomic extent: proctitis, left-sided colitis or pancolitis.
    - Endoscopy findings:

- Normal or inactive disease
- Mild disease (erythema, decreased vascular pattern, mild friability)
- Moderate disease (marked erythema, lack of vascular pattern, friability erosions)
- Severe disease (spontaneous bleeding, ulceration).
- For CD patients:
  - Harvey-Bradshaw Index (HBI) (a simplified version of CDAI)
  - General disease activity:
    - Mild to moderate: ambulatory patients able to tolerate oral alimentation without manifestations of dehydration, toxicity, abdominal tenderness, painful mass, obstruction or >10% weight loss.

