- Non severe (Remission <5; Mild disease 5-7; Moderate disease 8-16)
- Severe disease >16

Partial Mayo Index Score

- Non severe (Remission = 0-1; Mild Disease = 2-4; Moderate Disease = 5-7)
- Severe Disease =8-9

We will compare the percentage of patients reporting each co-morbidity between IBP severe or non-severe using Chi-Square.

A logistic regression analysis will be performed, in which **IBP severe or non-severe at baseline** will be used as the dependent variable and patient disease (CD or UC) and different comorbidities variables will be used as independent variables, yielding the following results: Odds Ratio, 95%CI, p-value, sensitivity and specificity.

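### The 2-point-fall rule labels any index-classified patient with baseline PMS 0-1 or HBI 0-1 a non-responder by arithmetic, so it can misclassify the outcome of the primary models

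*SAP*

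**What the plan says.** **Outcome rule.** SAP 7.1 and Protocol 6.4.5 make a non-responder of a CD patient "not achieving a reduction in HBI of at least 2 points from baseline for CD". For UC, response requires "a decrease in the PMS of at least 2 points for UC". SAP 7.1 uses the same threshold for primary non-response (10 weeks) and for loss of response (at least 6 months).

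**Fallback.** "In the cases where these indexes are not available, clinical response will be evaluated according to physician criteria at short term", with a parallel long-term judgement. Unavailability of the index is the only trigger.

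**Eligibility.** The criterion closest to disease status is "Patients naive to biologics that started treatment with biologics between June 2011 and June 2013". Neither Protocol 6.3.2-6.3.3 nor SAP 3.7-3.8 sets a minimum PMS or HBI.

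**Baseline bands.** SAP 7.3 groups baseline PMS as "Non severe (Remission = 0-1; Mild Disease = 2-4; Moderate Disease = 5-7" and baseline HBI as "Non severe (Remission <5; Mild disease 5-7; Moderate disease 8-16". The PMS is described in Protocol 6.4.4 as "Partial Mayo Score (PMS) (9 point scale that excludes the endoscopic appearance of the mucosa".

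**Timing of the indexes.** Protocol 6.4.4 collects "Disease activity at the beginning of the reference period and at the study visit through collection of the following variables". It lists no week-10 collection.

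**Loss of response.** Protocol 6.4.5 confines it to patients with an initial response. The variable defined in SAP 7.1 carries no such restriction.

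**The concern.** A change score with a fixed threshold has a floor. A patient whose baseline is lower than the required fall cannot meet it, whatever the drug does. The rule treats a patient who begins in the SAP's PMS remission band and stays there in the same way as one whose disease failed to improve.

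Nothing else in the plan catches these patients. They are eligible, a low baseline does not send them to physician criteria, and baseline PMS or HBI is not among the candidate variables in SAP 7.2.

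The affected label is the dependent variable of both primary logistic models and of both extraintestinal-manifestation models in SAP 7.3. If patients below the floor are spread evenly over comorbidity groups, odds ratios are diluted. If they are not, a comorbidity can appear to predict non-response, or to protect against it, only because it goes with a low starting index.

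**Working it through.** **1. Where the label is forced.** The largest possible fall from baseline b on a scale with minimum 0 is b, so non-response is forced when b < 2.
- PMS: minimum 0 (from the SAP 7.3 band). Forced at 0 and 1, which is exactly the SAP's remission band.
- HBI: minimum 0 is assumed, as the documents do not state it. Forced at 0 and 1. The rest of the HBI remission band (2-4) can still fall by 2.

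**2. The plan's own sample size.** Protocol 7.1 uses 10 events per variable, at most 10 variables and 50% non-response: 10 × 10 / 0.50 = 200 per disease. The stated figure is reproduced.

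**3. Inputs for the size of the effect.**
- p = non-response above the floor = 0.50 (Protocol 7.1). As an alternative, p = 0.30, because Protocol 4 puts primary non-response to anti-TNF at up to 30%.
- f = share of index-classified patients with baseline 0-1. The documents do not give it, so a range is assumed.
- Observed non-response q = f + (1 − f) × p. Observed odds ratio = [q1/(1 − q1)] / [q0/(1 − q0)], where 1 is with and 0 without the comorbidity.

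**4. Equal shares, p = 0.50, per 200 patients.** Observed q = 0.50 + 0.50f. Events above the floor = 200 × (1 − f) × 0.50. For a true odds ratio of 2.00, p1 = 2/3.

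| f | Forced | Observed non-response | Forced share of non-responders | Events above floor | True OR 2.00 becomes |
|---|---|---|---|---|---|
| 2% | 4 | 51.0% | 3.9% | 98 | 1.98 |
| 5% | 10 | 52.5% | 9.5% | 95 | 1.95 |
| 10% | 20 | 55.0% | 18.2% | 90 | 1.91 |
| 20% | 40 | 60.0% | 33.3% | 80 | 1.83 |

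Example at 10%: q1 = 0.10 + 0.90 × 2/3 = 0.70 (odds 2.333), q0 = 0.55 (odds 1.222), and 2.333 / 1.222 = 1.91.

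**5. Unequal shares, true odds ratio 1.** At p = 0.50 the observed odds reduce to (1 + f)/(1 − f).

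| f with vs without comorbidity | OR at p = 0.50 | OR at p = 0.30 |
|---|---|---|
| 15% vs 5% | (1.15/0.85)/(1.05/0.95) = 1.22 | (0.405/0.595)/(0.335/0.665) = 1.35 |
| 20% vs 5% | (1.20/0.80)/(1.05/0.95) = 1.36 | (0.440/0.560)/(0.335/0.665) = 1.56 |
| 5% vs 10% | (1.05/0.95)/(1.10/0.90) = 0.90 | (0.335/0.665)/(0.370/0.630) = 0.86 |

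**6. Which patients reach the index rule.**
- *Primary non-response:* the rule needs a week-10 index. None is scheduled, so it applies only where the chart happens to hold one. The others go to physician criteria.
- *Loss of response:* the study-visit index is scheduled, so the rule can readily apply. Under SAP 7.1 a patient below the floor is then coded as loss of response. Under Protocol 6.4.5, one who was index-classified at short term cannot be an initial responder and leaves the analysis. Neither route reflects what happened to the patient.

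**The case against.** **Few patients may be involved.** Protocol 4 describes biologics as used in moderate to severe CD and acute severe UC, which points to few baselines of 0-1. The SAP bands only collapse the index into severe and non-severe, and give no expected count. This stands: the size is unknown, and the unequal shares above are illustrations with no basis in the documents. Even the direction of bias is open.

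**Not every patient with a low baseline is affected.** A reader might infer that all of them are coded as non-responders in both models. The documents do not support that. With no scheduled week-10 index, many primary non-response calls may be made by the physician. For loss of response, the Protocol definition and the comparison groups named in SAP 7.2 suggest initial responders only. The point holds for index-classified patients and, for loss of response, depends on which definition is followed.

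**Adjustment could help.** A reader might also infer that no baseline adjustment can repair the bias. That is too strong. A group with a fixed outcome carries no information on the comorbidity effect, so conditioning on an indicator for baseline below 2 leaves the odds ratio to patients above the floor and removes this bias. A linear baseline term would correct it only in part, and the crude non-response rate stays inflated in either case. The plan as written contains neither term.

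**Conclusion.** The concern holds for patients classified by the index. The stated rule gives them a label fixed by their baseline, which is wrong for those who remained well, and no other provision removes it. It can reach both primary models and both extraintestinal-manifestation models.

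The mechanism is certain for PMS. For HBI it rests on an assumed minimum of 0. The size is not known: a few percent below the floor, evenly spread, changes little (a true odds ratio of 2.00 becomes 1.95 at 5%), while 10-20%, or shares that differ by comorbidity, would matter (0.90 to 1.36 in place of 1 in the illustrations at 50% non-response). The documents do not support saying that the primary outcome is badly misclassified, only that it can be and that the plan has no means of showing how often. The mismatch between Protocol and SAP on loss of response decides whether these patients are miscoded or dropped, and needs settling with it.

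**What to change.** In both SAP 7.1 and Protocol 6.4.5:
- Apply the index rule only where a 2-point fall is possible (baseline PMS ≥ 2, HBI ≥ 2), and state the HBI minimum.
- Classify the other patients by the physician criteria already in the plan, or as not evaluable where no physician judgement of response is recorded. Protocol 6.4.4 lists a physician's global assessment, but it grades disease activity, and the documents do not show that a response judgement is recorded when an index exists.
- Use one definition of loss of response, saying whether it is limited to initial responders.

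In the analysis:
- Report the number with baseline below 2 by disease and comorbidity status.
- Repeat both primary models without these patients, and again above the SAP's remission bands (PMS > 1, HBI ≥ 5).

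The cost is a sentence or two in each document, slightly fewer index-classified patients and an added sensitivity run. If no physician judgement exists for these patients, some events are lost: at an assumed 10%, 90 informative events per 200 patients in place of the planned 100. No new data collection is needed, and the SAP is due to be signed before database lock, so the rule can be set in time.

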## 6. Methodology

### 6.1. Study design

In order to meet the objectives of the present study, a retrospective, non-interventional, multicentre observational study including 25 gastroenterology sites from all around Spain has been designed. Participating investigators will be gastroenterologists and will include consecutive patients diagnosed with UC or CD that started treatment with biologics between June 2011 and June 2013, after giving written informed consent. The study will consist of one only visit in which investigators will collect patients' sociodemographic (age, gender, race, level of education, smoking habits alcohol intake) and clinical (concomitant diseases, date of diagnosis, previous treatment, current treatment, disease activity when starting treatment with biologics and at the study visit, current situation in terms of treatment with biologics) data from medical charts or directly from patients (in case of discrepancy, the information coming from medical charts will be preferable). Time since patients started biological treatment until study visit or until lack of treatment response or until treatment change will constitute the reference period for the study. In order to fulfill current legislations regarding non-interventional studies, investigators will commit to follow usual clinical practice.

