#### 6.4.5. Main outcome

Non responders will be those patients not achieving a reduction in HBI of at least 2 points from baseline for CD, and a decrease in the PMS of at least 2 points for UC.. In the cases where these indexes are not available, clinical response will be evaluated according to physician criteria at short term (10 weeks after starting the anti-TNF) and at long term (at least 6 months after starting the anti-TNF). Primary non-responders (PNR) were defined as patients with no clinical response at short term. Loss of response (LOR) was defined as loss of the effect of the drug along the follow up in a patient with initial response.

Reasons to stop the drug will be classified as follows: PNR, LOR, side effects (SE), remission and other.

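### SAP 7.1 lets index availability choose the response criterion separately at week 10 and later, so some patients can be coded as loss of response, or as maintained, against what was recorded for them

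*SAP*

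**What the plan says.** SAP 7.1 defines two outcomes, which become the dependent variables of the two primary logistic models in SAP 7.2 and of the extraintestinal-manifestation models in SAP 7.3.

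- **Primary non-response:** "Those patients who 10 weeks after starting the anti-TNF not achieving a reduction in HBI of at least 2 points from baseline for CD", with a matching PMS rule for UC.
- **Loss of response (LOR):** "Those patients who at least 6 months after starting the anti-TNF not achieving a reduction in HBI of at least 2 points", again measured from baseline and with a matching PMS rule. The definition sets no condition that the patient responded first.
- **Fallback:** "In the cases where these indexes are not available, clinical response will be evaluated according to physician criteria at short term". The general paragraph gives it once for both horizons, and it is then repeated under each outcome. Under LOR it names the short-term assessment, although the general paragraph pairs maintenance and loss with the long-term one.

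Protocol 6.4.5 defines the second outcome differently: "Loss of response (LOR) was defined as loss of the effect of the drug along the follow up in a patient with initial response".

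On data collection, Protocol 6.4.4 lists "Disease activity at the beginning of the reference period and at the study visit through collection of the following variables", which include HBI and PMS. Protocol 6.1 gives the same two times: "disease activity when starting treatment with biologics and at the study visit". The clinical variables come from "medical records (when available) or directly from patients during the study visit".

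**The concern.** LOR is a change within a patient: a response, then its loss. Under SAP 7.1 the two ends of that change can be measured by different criteria, and which criterion applies depends on what happens to be in the chart. Part of the outcome would then be disagreement between physician and index, not loss of drug effect.

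One of the two primary models is at stake. SAP 7.2 screens candidate variables at p<0.1 against this outcome and then applies stepwise selection, so misclassification affects both which comorbidities enter the model and the size of their odds ratios.

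**Working it through.** **1. The plan's own figure.** Protocol 7.1 uses 10 events per variable, 10 variables and 50% response: 10 × 10 / 0.50 = 200 per disease. This reproduces and does not depend on the point made here. The documents give no expected LOR proportion and no physician–index agreement rate, so every rate below is an assumption.

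**2. Which criterion applies when.**

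| Time | Index in the protocol's variable list? | Criterion under SAP 7.1 |
|---|---|---|
| Start of biologic | Yes, if in the chart | Baseline |
| Week 10 | Not listed | Index if found, otherwise physician |
| 6 months or later | Yes, at the study visit | Index if baseline and visit values exist, otherwise physician |

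Patients started by June 2013 and the protocol cites a 2016 publication, so the study visit lies well beyond six months. The mismatch needs three things together: a baseline index, no week-10 index, and a later index.

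**3. Two patients traced through the rules (invented values).**

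- *No loss recorded.* HBI is 8 at start (moderate in the SAP 7.3 bands), the physician records response at week 10, and HBI is 7 at the visit. First model: responder. Second model: the fall is 8 − 7 = 1, below 2, so LOR. With two readings, a fall that never reached 2 points cannot be told from one that did and then reversed.
- *Loss overridden.* HBI is 12 at start, the physician records response and later loss, and HBI is 9 at the visit. The fall is 12 − 9 = 3, so the patient is coded as maintained.

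**4. Illustration of size, first type of error only.** Let t be true LOR among initial responders and d the share of continuing responders coded LOR by the index. Assume t = 30% (in patients without the comorbidity), d = 5–20% and equal across groups, and every responder exposed to the mismatch.

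Observed LOR = t + (1 − t)d. False share = (1 − t)d / observed LOR.

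For a true odds ratio of 2.0, the odds without the comorbidity are 0.30/0.70 = 0.429. With it they are 0.857, so true LOR is 0.857/1.857 = 46.2%.

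| d | Observed LOR, no comorbidity | False share | Observed LOR, comorbidity | Estimated OR |
|---|---|---|---|---|
| 5% | 0.30 + 0.70 × 0.05 = 33.5% | 0.035/0.335 = 10% | 48.8% | 1.90 |
| 10% | 37.0% | 0.070/0.370 = 19% | 51.5% | 1.81 |
| 20% | 44.0% | 0.140/0.440 = 32% | 56.9% | 1.68 |

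**5. Sensitivity to the assumptions.**

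- *Half of responders exposed.* Effective d is 2.5–10%. Observed LOR is 31.8–37%, the false share 5.5–19%, and the estimated OR 1.94–1.81.
- *Both errors present.* With d = 5% and 20% of true losses overridden: 0.30 × 0.80 + 0.70 × 0.05 = 27.5%, which is below the true 30%.
- *Error differs by comorbidity.* With true OR 1.0, d = 10% without and 20% with the comorbidity: (0.44/0.56)/(0.37/0.63) = 1.34. With the two values exchanged, the result is 0.75.

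**6. The missing condition on initial response.** Read literally, the SAP 7.1 LOR definition also admits primary non-responders. Of 400 patients that would be 200 at the 50% response in Protocol 7.1, or 120 at the 30% primary non-response mentioned in Protocol 4. SAP 7.2 compares maintained response with loss of response, which suggests that they are meant to be excluded, but no rule says so.

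**The case against.** The strongest reply is that the fallback can be read per patient. Protocol 6.4.5 and the general paragraph of SAP 7.1 use one sentence for both horizons, which could mean that a patient without usable indexes is judged by the physician throughout. The text allows this. However, SAP 7.1 then repeats the fallback inside each outcome definition, and taken literally that makes the choice time point by time point.

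A reader might infer that week-10 response will nearly always be physician-judged. The documents do not establish that. The eCRF is not among them, and the SAP's week-10 index rule suggests that some values were expected. The protocol's variable list is not exhaustive either: it names no week-10 physician response item, although the SAP needs one. Historical baseline indexes may also be missing, in which case the physician judges both ends and no mismatch arises.

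A reader might also infer that LOR will be overstated and odds ratios pulled towards 1. Step 5 shows that neither follows: the override error works the other way, and unequal error can move an odds ratio in either direction.

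Finally, making physician judgement the main criterion would not be a clear improvement. The index is the SAP's first choice, and physicians who know the comorbidities may judge those patients differently. That argument stands, and it is why the remedy adds an analysis without replacing the criterion.

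**Conclusion.** The point holds as a defect in the stated rule. SAP 7.1 allows a different criterion at each time point and defines LOR as a state relative to baseline. Protocol 6.4.5 defines it as "loss of the effect of the drug along the follow up in a patient with initial response". Where baseline and visit indexes exist but a week-10 index does not, a physician-judged responder can be coded LOR with no recorded loss, and a physician-recorded loss can be coded as maintenance.

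The number of patients affected and the net direction of error in the LOR proportion are unknown. The range of 33.5–44% observed LOR, with an odds ratio of 2.0 estimated as 1.90–1.68, rests on assumed values: 30% true LOR, full exposure, 5–20% misclassification equal across groups, and no error in the other direction. It shows what the rule could do and does not forecast the result. The effect shrinks if fewer patients are exposed. The change is worth making before database lock because the outcome is primary and the correction is cheap.

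**What to change.** In SAP 7.1–7.2:

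1. Restrict the LOR model to patients with an initial response, as Protocol 6.4.5 requires, and change the LOR fallback from the short-term to the long-term physician assessment so that it matches the general paragraph. This settles who enters the model. It does not remove the mismatch, since the HBI 8-to-7 patient above still enters.
2. Tabulate patients by the criterion used at week 10 and at six months or later (index–index, physician–physician, physician–index, index–physician), by disease.
3. Pre-specify an LOR analysis that uses the same criterion at both times, index–index or physician–physician, reported beside the mixed-criterion result. State that a comorbidity association seen only under the mixed rule will not be interpreted as loss of response.

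**Cost.** This is mainly SAP wording and a table. The physician's long-term category, which the SAP already names, must be recorded for physician-judged responders. The LOR set becomes smaller. With 400 patients pooled and 50% response there are 200 initial responders; at an assumed 30% LOR that is 60 events, or 6 variables under the 10-per-variable rule in Protocol 7.4. The same-criterion set may be smaller still and will rest more on physician judgement, so both results should be shown.
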